Despite these suggested therapeutic benefits of combined thermal ablation and embolization techniques, little is known about the prognostic effects of MWA + TAE in early-stage HCC. To our knowledge, no RCTs have compared the combination therapy (MWA + TAE) with monotherapy (MWA alone) in this selective cohort. The efficacy of MWA in combination with TAE as a prophylactic treatment to reduce recurrence in HCC patients with a small tumor burden is unknown. Moreover, the optimal protocol and timing for MWA combined with TAE as a treatment for early stage HCC has yet to be determined. For all of these reasons, RCTs are required to examine the feasibility as well as the possible therapeutic and/or survival benefits of combination MWA + TAE in selected patients with early-stage HCC.

STUDY DESIGN

Objective

This single-center, prospective RCT is designed to compare the outcomes and clinicopathologic results of blunt transarterial embolization (TAE) and microwave ablation (MWA) combination therapy with MWA monotherapy for the treatment of early (stages 0 and A) hepatocellular carcinoma (HCC). The primary aim of this study is to test the following hypothesis: 2-year intrahepatic disease-free survival does not differ between patients receiving the experimental therapy (MWA + TAE) and patients receiving the standard therapy (MWA alone) as treatment for early-stage HCC. Secondary aims are: 1) to determine the clinical feasibility of TAE + MWA in HCC patients with a small tumor burden using patient demographics and disease characteristic data and 2) to determine the effect of TAE on radiographic tumor characteristics in this patient cohort.

The primary outcome is 2-year intrahepatic disease-free survival, which is measured from time of randomization and is defined as the absence of local or regional recurrence of HCC as determined by diagnostic imaging. *Local recurrence* is defined as an enhancing lesion contiguous with the ablation zone that is present on subsequent imaging but was not present on the initial postablation scan. *Regional recurrence* is defined as hepatic recurrence that is not adjacent to the ablation site.

Secondary outcome measures include:

- Patient and disease characteristics (Table 1)
- 1-year, 2-year, 3-year, and 5-year overall survival;
- 1-year, 3-year, and 5-year intrahepatic disease-free survival;
- Number of TAE procedures required (for multilobar lesions or repeat effect)

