with either an open, laparoscopic, or robot-assisted laparoscopic approach. **The expected enrollment rate is 2 patients/month.**

Patients diagnosed with primary HCC classified as stage 0 (very early) or stage A (early) will be considered for inclusion in this study. Tumors will be staged preoperatively with computed tomography (CT) and/or magnetic resonance imaging (MRI). Laparoscopic ultrasound will be performed intraoperatively.

Eligible patients will meet the following inclusion criteria:

- Male or female patients aged ≥ 18 and ≤ 75 years
- Primary diagnosis of HCC according to the guidelines published by the American Association for the Study of Liver Diseases (AASLD)²⁸ and the diagnostic criteria used by the European Association for the Study of the Liver (EASL)²⁹:
 - Two imaging techniques showing typical features of HCC; or
 - Cytologic/histologic diagnosis of HCC; or
 - Radiographic classification as LIRAD 5 (Appendix III), regardless of AFP level.
- HCC classification of stage 0 (very early) or stage A (early) according to BCLC staging system criteria (Appendix I):
 - Solitary HCC lesion < 3 cm in diameter
 - ≤ 3 HCC lesions, each ≤ 3.0 cm in diameter
- Total bilirubin level, with or without portal hypertension, less than or equal to 3.0.
- Adequate clinical condition to undergo laparoscopic or robot-assisted laparoscopic TAE and/or MWA as treatment for HCC
- Willing and able to give informed consent

Patients meeting the inclusion criteria will be subjected also to the following exclusion criteria:

- Radiologic (CT or MRI) evidence of invasion into major portal/hepatic venous branches and no extrahepatic metastases (LR-5V or LR-M radiologic classifications)
- Evidence of residual disease at first post-MWA CT examination
- Body Mass Index (BMI) > 35
- Previous history of hepatic resections
- Severe renal dysfunction (creatinine clearance of < 40 mL/min)

- Pregnant or nursing women

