According to a computer-generated variable size blocked randomization method, eligible patients will be allocated on a 1:1 basis to receive the experimental therapy (MWA + TAE) and standard therapy (MWA alone), respectively. The nature of the treatments and their possible adverse effects preclude the use of double-blind and double dummy techniques. In patients randomized to receive the experimental therapy, TAE treatments will be initiated within one week of randomization, then followed by MWA within 4 to 6 weeks after reviewing radiological scans from TAE. MWA will be performed 4 to 6 weeks following randomization in MWA standard therapy groups. Treatment may be discontinued if any exclusion criteria develop in the patient or at the patient's request.

Sample Size

Power calculations are based upon expected 2-year survival rates. The main endpoint is 2-year intrahepatic disease-free survival, measured from the time of randomization which is measured from time of randomization and is defined as the absence of local or regional recurrence of HCC as determined by diagnostic imaging. Considering an estimated 80% and 90% intrahepatic disease-free survival at 2 years of follow-up for patients receiving MWA alone and MWA + TAE combination therapy, respectively, a sample size of 92 patients is required to detect a clinically meaningful 10% absolute difference in 2-year peritoneal disease-free survival with MWA + TAE with a minimum of 95% power and a 2-sided $\alpha = .05$. To account for a 5–10% withdrawal rate (following intraoperative detection of vascular invasion or extrahepatic metastasis, etc.), a sample size of 100 patients is required (50 patients per arm). If the rate of patient enrollment is suboptimal, a covariate adaptive randomization method will be used to allocate patients in a 2:1 ratio to receive experimental therapy (MWA + TAE) and standard therapy (MWA alone), respectively, which would result in an overall sample size of 83 patients.

Clinical Procedures

Preprocedural Strategy

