Before randomization, patients will be assessed with either MRI or triphasic CT imaging and evaluated for baseline liver function, hematology, coagulation studies, and serum AFP. Liver function and underlying disease burden will be staged with the Child-Turcotte-Pugh criteria and the BCLC classification, respectively (Appendix IA and B). Radiologic findings will be reported according to the LI-RADS criteria. Patient demographics, histologic analysis, and assessment of portal vein hypertension and its sequelae will also be recorded. Patients will receive pre-operative counseling.

Carolinas Medical Center follows already established Enhanced Recovery After Surgery (ERAS) SMART™ protocol for the pre-, intra-, and postoperative care of patients undergoing certain procedures in the hepatopancreatobiliary Division. Division-specific standard guidelines will be applied to the care of patients included in this study.

Procedural Strategy

For MWA and TAE procedures, patients will be given general anesthesia. In patients randomized to receive the experimental therapy, TAE treatments will be initiated within one week of randomization, then followed by MWA within 4 to 6 weeks after reviewing radiological scans from TAE. MWA will be performed 4 to 6 weeks following randomization in standard MWA therapy groups. Treatment may be discontinued if any exclusion criteria develop in the patient or at the patient's request.

For TAE procedures, moderate/procedural or general anesthesia will be induced. A selective 5-F catheter will be introduced into the femoral vein, and visceral angiography will be performed to assess the arterial blood supply to the liver and to the lesion(s) identified on preprocedural imaging. All patients will undergo a distal super-selective catheterization of the hepatic arteries using a coaxial technique and microcatheters. Embolization will be performed with LC beads from BTG with a maximum size of 700 µm. The LC beads will be admixed with 8-15 mL of contrast and injected into the arterial branch at a rate of 1-2 mL/min. After embolization, angiography will be performed to determine the extent of vascular occlusion and to assess collateral tumor arterial supply. Patients will be observed carefully, and analgesia (morphine or meperidine) will be administered if necessary. Given the small tumor size included in this study, bilobar lesions will be treated sequentially during the same interventional procedure.

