All operative MWAs will be performed in a laparoscopic or robot-assisted laparoscopic setting by one of four hepatobiliary surgeons with extensive experience with intraoperative US guidance and hepatic ablation ([name]). Care will be taken to create ample distance between the microwave near-field and any adjacent structures (diaphragm/heart, stomach/esophagus, colon, duodenum, gallbladder) by mobilization of the liver. All ablations will be guided by intraoperative ultrasound (BK Medical A/S, Herlev, Denmark) with care taken to allow for complete tumor treatment while preserving adequate distance between the microwave near-field and adjacent intrahepatic structures (portal pedicles, hepatic veins). Ablations will be performed with a 2.45-GHz generator with a 1.8-mm-diameter transcutaneous antenna (Acculis pMTA Accu2i; AngioDynamics Inc., Denmead, Hampshire, UK).

Operative variables will be recorded per patient, and individual ablation characteristics including tumor location by hepatic segment, proximity to a portal pedicle, number of applications, power settings, and ablation duration will be recorded for each individual tumor. A clearly demarcated zone of color flow Doppler activity will be visualized within 30 s of initiating the ablation to assure that the target is within the microwave ablation zone. Patients will be observed carefully, and analgesia will be administered per standard protocol if necessary.

Postprocedural Strategy

Division-specific standard guidelines will be applied to the postoperative care of patients included in this study. Postoperative complications will be recorded and treated symptomatically. All patients will be closely followed up for disease progression with clinical and laboratory examinations 4–6 weeks after ablation/TAE procedures, then every 3 months for the first 2 years. At 4–6 weeks following TAE +/- MWA procedures, tumors will be assessed radiographically and characteristics will be reported according to the LI-RADS criteria and guidelines. Imaging techniques will then be performed every 3 months during the first 2 years postoperative and every 6 months afterward. In addition, AFP levels will be obtained every 3 months during the first 2 years postoperative and every 6 months afterward.

Data Collection

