Patients alive at the time of analysis will be censored at the last follow-up examination or at liver transplantation. Univariate analyses will be performed using the log-rank test of equality for categorical variables and the chi-square test with Cox proportional hazard model for continuous variables to identify clinical variables (Child–Pugh class, Okuda class, Model for End-Stage Liver Disease (MELD) score, etiology of cirrhosis), tumor factors (extrahepatic disease, multicentric disease, tumor size, Milan criteria, AJCC tumor stage, AFP level), and treatment-related factors (TAE, complications, recurrence) predicting intrahepatic disease-free and overall survival. Survival and disease-free survival will be estimated using the Kaplan–Meier method and tested with the log-rank test following the intention-to-treat principle. Statistical analysis will be performed using SAS software (SAS Institute, Cary, NC, USA).

The analysis will be planned at a median follow-up of two years, with an interim analysis scheduled for 1 year after the first patient is enrolled or when 50% of total expected enrollment has been reached.

To improve patient selection in the future, additional exploratory analyses will be performed to identify potential prognostic factors. Table 1 details variables that will be included in a Cox proportional hazards regression model to obtain hazard ratios and 95% confidence intervals (CIs). All P values will be two-sided and a p value $< .05$ will be considered significant.

ETHICAL AND SAFETY CONSIDERATIONS

Protection of Patients

The techniques and procedures used in this study protocol are not investigational or provisional in nature; rather, they are established in the provision of care for patients of the HPB Division at Carolinas Medical Center. The therapeutic benefit of combination of TAE/MWA treatment in this patient population remains unknown and is the focus of this study. The additive risk for adverse events is expected to be equal to the individual risks of the study procedures in this protocol.

Standard Division-specific guidelines will be closely followed to ensure patient safety and clinical well-being during all procedures. Patients will be closely monitored for complications associated with MWA and TAE, including wound complications, hematologic toxicities, and others.

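### An exclusion criterion read from the first post-MWA scan is known only after randomization; its analysis status is not reconciled with intention-to-treat, and residual border tumour is not itself a primary event

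*Combined protocol and SAP*

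**What the plan says.** The exclusion criteria under Patient Eligibility and Allocation list "Evidence of residual disease at first post-MWA CT examination". The same section randomizes eligible patients and places the procedures afterwards: "MWA will be performed 4 to 6 weeks following randomization in MWA standard therapy groups". In the combination arm, TAE starts within a week of randomization, "then followed by MWA within 4 to 6 weeks after reviewing radiological scans from TAE". Under Postprocedural Strategy, at 4-6 weeks "following TAE +/- MWA procedures, tumors will be assessed radiographically".

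For a patient who meets an exclusion criterion later, the text says "Treatment may be discontinued if any exclusion criteria develop in the patient" (Patient Eligibility and Allocation, repeated under Procedural Strategy). It does not mention follow-up or analysis. Under Statistical Analysis, survival and disease-free survival are "tested with the log-rank test following the intention-to-treat principle".

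The primary endpoint counts local or regional recurrence (Objective; Definitions). Local recurrence is a lesion touching the ablation zone that is "present on subsequent imaging but was not present on the initial postablation scan". Regional recurrence must lie away from the ablation site. Definitions also names incomplete ablation (residual tumour at the border on the initial scan), expected residual disease (disease deliberately left untreated at the initial MWA session), and secondary ablation for incomplete ablation.

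**The concern.** An eligibility rule should be decidable at randomization. This one, applied to the trial's own MWA, depends on how well the randomized treatment worked. TAE before MWA may change how often ablation is complete: the Background gives higher complete response as one aim of combining embolization with ablation. Removing patients on this criterion could therefore remove different kinds and numbers of patients from each arm, and the comparison would no longer be of the groups as randomized.

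Keeping everyone does not close the matter. Residual border tumour falls between the two recurrence definitions, so failure to clear the tumour is not registered by the primary endpoint. Any gain or loss in complete ablation would not show there. If the choice stays open until data are seen, the analysis set of the primary comparison can be settled with knowledge of the result.

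**Working it through.** **When the criterion can be judged (weeks after randomization).**
- Standard arm: MWA at 4-6, scan 4-6 later: 4+4 to 6+6 = 8-12.
- Combination arm, MWA counted from TAE: 0+4+4 to 1+6+6 = 8-13.
- Combination arm, MWA counted from review of a scan taken 4-6 weeks after TAE: 0+4+4+4 to 1+6+6+6 = 12-19.

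On every reading the scan follows randomization, and it may be later in the combination arm.

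**Is residual border tumour an event?** Local recurrence must be absent on the initial post-ablation scan; residual tumour is present on it. Regional recurrence must not be adjacent to the ablation site; border tumour is. It meets neither definition. A later qualifying recurrence in the same patient would count.

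**Which way does the text point on removal?** Towards keeping: the intention-to-treat statement, a discontinuation sentence limited to treatment, and the foreseen re-ablation. Towards removal: the item's place in the exclusion list, and the Sample Size allowance of 5-10% for withdrawals, whose named reasons are found during the operation and so after randomization. The step from 92 to 100 fits about 8% (92/0.92 = 100).

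**Size.** The plan's own figure is the starting point: "Considering an estimated 80% and 90% intrahepatic disease-free survival at 2 years of follow-up", so 90 - 80 = 10.0 points. The rest is assumption. Let rC and rT be the residual rates with MWA and MWA+TAE, and take 80% and 90% as the 2-year rates among completely ablated patients.
- Dropped: 0.90 - 0.80
- Kept, no event: [0.90(1-rT)+rT] - [0.80(1-rC)+rC]
- Residual as failure (not the protocol's definition): 0.90(1-rT) - 0.80(1-rC)

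| rC / rT | Dropped | Kept, no event | Residual as failure | Dropped minus kept | Dropped minus failure | Kept minus failure |
|---|---|---|---|---|---|---|
| 10% / 5% | 10.0 | 90.5-82.0 = 8.5 | 85.5-72.0 = 13.5 | 1.5 | -3.5 | -5.0 |
| 10% / 2% | 10.0 | 90.2-82.0 = 8.2 | 88.2-72.0 = 16.2 | 1.8 | -6.2 | -8.0 |
| 5% / 5% | 10.0 | 90.5-81.0 = 9.5 | 85.5-76.0 = 9.5 | 0.5 | +0.5 | 0 |
| 10% / 10% | 10.0 | 91.0-82.0 = 9.0 | 81.0-72.0 = 9.0 | 1.0 | +1.0 | 0 |
| 5% / 8% | 10.0 | 90.8-81.0 = 9.8 | 82.8-76.0 = 6.8 | 0.2 | +3.2 | +3.0 |

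If kept patients later have a qualifying recurrence at their arm's own 20% or 10%, the difference returns to 10.0 throughout. With 50 per arm, 50(rC+rT) gives 7.5, 6, 5, 10 and 6.5 residual patients, against 50(0.20)+50(0.10) = 15 planned events.

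More extreme pairs widen the ranges. In the order dropped, kept, failure, 15%/5% gives 10.0, 7.5 and 17.5; 5%/10% gives 10.0, 10.0 and 5.0.

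Three limits apply. Sample Size states 80%/90% for patients receiving each therapy, not for the completely ablated. Dropping gives 10.0 by construction, so this model cannot measure selection bias. It uses 2-year proportions, while the planned test is log-rank. Whether 92 follows from the stated power is a separate question that does not enter here.

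**The case against.** The strongest reply is that intention-to-treat is the only explicit analysis rule and already answers the question: stopping treatment is not leaving the analysis, and planned re-ablation presumes continued follow-up. Much of this stands. A reader might infer that the protocol drops residual cases; it nowhere says so. What remains is that an exclusion item and a withdrawal allowance sit beside that rule with no sentence joining them.

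The item may also concern only an ablation before enrolment, since Table 1 records prior therapy. That is possible but unstated, and the neighbouring item on hepatic resection is expressly worded as past history while this one is not.

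A reader might also infer that the ambiguity moves the result by 3 to 8 points in either direction. The documents do not support that. Shifts of that size are measured against residual-as-failure, which the protocol does not define as an event, and in the five pairs every shift above 3.2 points is downward. The two readings the text permits lie within 1.8 points, small beside a standard error of about 7.1 points (sqrt(0.16/50 + 0.09/50) = 0.0707).

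Nor do the documents show the endpoint to be wrong. The Background frames the question as reducing recurrence, so a recurrence-only endpoint may be deliberate, and LI-RADS findings at 4-6 weeks after ablation are already a secondary outcome.

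Finally, the CONSORT diagram (Figure 1) and the content of Appendices IV and V are not visible in the text available and could bear on handling.

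**Conclusion.** The concern holds in a limited form. For the trial's own MWA the criterion is a post-randomization result. Followed literally as an exclusion, it would contradict the intention-to-treat analysis; if it is not followed, unintended border residual goes uncounted unless a qualifying recurrence comes later. The text leans towards keeping these patients without settling it.

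Under the five assumed pairs, the permitted readings differ by 0.2-1.8 points. Compared with counting residual as failure, the difference shifts by 0 to 1.0 point with equal residual rates, and by -3.5 to -8.0 or +3.0 to +3.2 points with unequal rates. These ranges belong to the assumed pairs and to reading 80%/90% as rates after complete ablation; neither the true size nor the direction can be fixed from the documents. Because the defect is one of principle, with a small effect between the permitted readings and a cheap remedy, I rank it below a must-fix.

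**What to change.** 1. State that the residual-disease item removes no randomized patient and that the primary set is all randomized patients. If it was meant only for an ablation before enrolment, say so.
2. Keep recurrence-only as primary if that is intended. Prespecify a sensitivity analysis that counts incomplete ablation (residual tumour at the ablation border) as an event, leaving out expected residual disease as the Definitions section uses that term. Use one dating rule for both arms, because an event dated at the scan could come later in the combination arm through scheduling alone. Report the incomplete-ablation rate by arm.
3. As an editorial correction, let disease-free survival time in Definitions run from randomization to first recurrence; it now runs to the absence of recurrence.
4. Reconcile the exclusion list, the discontinuation sentences and the Definitions section on treatment after residual disease. No clinical rule is proposed here.

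The cost is clarified wording and one added analysis; the 4-6 week scan is already scheduled. Making incomplete ablation a primary event is optional. It would require restating the 80%/90% assumptions, and absolute rates would look lower (72.0-76.0% versus 81.0-88.2% in the five pairs) and less comparable with recurrence-only reports.

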According to the GLOBOCAN 2008 estimates, over 749,000 new cases of liver cancer are diagnosed and 695,000 deaths from liver cancer occur worldwide each year¹. Hepatocellular carcinoma (HCC) accounts for 75-90% of the total liver cancer burden worldwide and most often occurs in the setting of chronic liver disease and cirrhosis². Surgical resection is the only treatment option that offers the potential of long-term survival; however, due to advanced, multifocal disease at diagnosis or lesions proximal to critical structures, fewer than 5% of patients are candidates for surgery. Overall 5-year survival following a diagnosis of HCC is <16%³.

Prognostic variables including tumor status (number and size of nodules, vascular invasion, and N1 and M1 staging), liver function (Child-Pugh's class, bilirubin, albumin, portal hypertension, ascites), and patient health (Eastern Cooperative Oncology Group (ECOG) performance status and symptomology) are used by the Barcelona-Clinic Liver Cancer (BCLC) guidelines for classification of HCC into 5 stages (0, A, B, C, and D) (Appendix I)⁴. This classification is intended to predict outcome and to enable appropriate treatment allocation for each HCC patient. Resection is recommended for patients with BCLC Stage 0 (very early) disease, which is characterized by the presence of a single tumor <2 cm in diameter without vascular invasion/satellites in patients with good health status (ECOG-0) and well-preserved liver function (Child-Pugh A class)⁴. However, resection does not address the precancerous remnant liver, especially in the setting of cirrhosis, where progressive organ decompensation and ongoing hepatocarcinogenesis often lead to recurrence. The rate of recurrence of HCC at 5 years post-surgery is 60–70%^{5,6}, and the majority of these recurrences are limited to the liver and develop in the first postsurgical year⁶. Clearly, more effective operative techniques and treatment modalities are needed to improve clinical outcomes of surgical resections for early-stage HCC.

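### Neither the 1:1 blocked allocation nor the primary log-rank test takes account of lesion number, a prognostic factor known before randomization; stratifying on it is a cheap but modest improvement

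*Combined protocol and SAP*

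**What the plan says.** Under Patient Eligibility and Allocation the main scheme reads: "According to a computer-generated variable size blocked randomization method, eligible patients will be allocated on a 1:1 basis". No stratification factor is attached to it. Covariate balancing appears once, under Sample Size, as a fallback for slow enrollment: "a covariate adaptive randomization method will be used to allocate patients in a 2:1 ratio". That fallback names no covariates.

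Lesion number varies among eligible patients. Besides solitary tumors, the inclusion criteria admit "≤ 3 HCC lesions, each ≤ 3.0 cm in diameter". The Background introduces the BCLC staging system with "Prognostic variables including tumor status (number and size of nodules, vascular invasion, and N1 and M1 staging", so number of nodules is on the plan's own prognostic list. Under Preprocedural Strategy, MRI or triphasic CT is done before randomization, so lesion number is known in time to be used.

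Under Statistical Analysis, survival and disease-free survival are compared by an intention-to-treat log-rank test with no strata or adjustment. Multicentric disease appears there only among the univariate prognostic analyses. Tumor number, listed in Table 1, enters only the exploratory Cox model.

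**The concern.** Blocking without strata balances the total number per arm and nothing else. Lesion number has a direct link to the primary endpoint as well as a prognostic one. The endpoint counts any local or regional recurrence in the liver, and local recurrence is defined at the ablation zone, so each further ablated lesion adds a site at which an event can occur.

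The trial is small: "a sample size of 100 patients is required (50 patients per arm". With few events, a visible excess of multi-lesion patients in one arm would make the result harder to interpret and open to argument, and the primary test as written has no means of accounting for it. Allocation cannot be repaired after patients are randomized, so the choice has to be made before enrollment.

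**Working it through.** **Inputs from the plan.** 50 patients per arm; 2-year intrahepatic disease-free survival of 80% on MWA alone and 90% on MWA + TAE (Sample Size); published recurrence of 10.5% to 24% after MWA (Background).

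**Assumptions.** The multi-lesion share π is not given, so 10% to 40% is shown. Block sizes are not given, so 2, 4 and 6 are used where needed. The published recurrence rates are not stated to be per lesion; treating them as independent per-lesion risks is an assumption.

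**1. The plan's own size and power.** For 80% versus 90%, 95% power and two-sided alpha .05, with mean rate 0.85:

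n per arm = [1.960·√(2·0.85·0.15) + 1.645·√(0.80·0.20 + 0.90·0.10)]² / 0.10² = (0.990 + 0.822)² / 0.01 ≈ 329, or 658 in total.

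The plan's 92 does not reproduce. Power is about 27% with 46 per arm and 29% with 50 per arm. That is a separate problem, but it sets the scale for any power gain below.

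**2. Expected events.** 50 × 0.20 + 50 × 0.10 = 15.

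**3. Chance imbalance without stratification.** Let K₁ and K₂ be the multi-lesion counts, each Binomial(50, π). A 10-point difference is 5 patients. At π = 0.30 the SD of the difference in shares is √(2·0.30·0.70/50) = 9.2 points. Exact probabilities:

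| Multi-lesion share | 10 points or more | strictly more than 10 points |
|---|---|---|
| 10% | 13% | 7% |
| 20% | 26% | 17% |
| 30% | 33% | 23% |
| 40% | 36% | 26% |

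Imbalances of 20 points or more occur in at most about 5% of trials over this range. With 46 per arm the chances of 10 points or more are 12%, 24%, 31% and 34%.

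**4. Imbalance with stratified blocks.** In 20,000 simulated trials of 100 patients at each share of 20%, 30% and 40%, the chance of a 10-point or larger imbalance fell from 25%, 32% and 34% to 0%. The reason is simple: an incomplete block of at most 6 leaves an excess of at most 3 patients in a stratum, and 3/50 is 6 points.

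**5. Effect of a 10-point imbalance on the estimate.** The local risk with k lesions is 1 − (1 − p)^k. At p = 0.105:

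- one lesion: 10.5%
- two lesions: 1 − 0.895² = 19.9%, an excess of 9.4 points
- three lesions: 1 − 0.895³ = 28.3%, an excess of 17.8 points

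A 10-point imbalance therefore shifts the 2-year difference by 0.10 × 9.4 = 0.9 to 0.10 × 17.8 = 1.8 points. The standard error of that difference is √(0.80·0.20/50 + 0.90·0.10/50) = 7.1 points, so the shift is 0.13 to 0.25 standard errors.

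**6. Power gain.** Three simulation runs of 5,000 to 8,000 trials per setting compared unstratified allocation and test with both stratified, for hazard ratios of 2, 3 and 5 between multi-lesion and solitary disease. At a ratio of 2 the gain was between nil and 1.6 points; at 3, between about 1 and 2.8; at 5, between about 2.5 and 4. Monte Carlo error was about 0.5 to 0.6 points per power figure. Type I error stayed near 5%.

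One run (8,000 trials per setting, 30% share) separated the two steps:

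| Hazard ratio | neither stratified | test only | both |
|---|---|---|---|
| 2 | 27.8% | 27.3% | 27.1% |
| 3 | 26.6% | 27.3% | 27.6% |
| 5 | 24.1% | 26.3% | 27.7% |

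The risk model in step 5 implies a ratio of 2 for two lesions and 3 for three, so 5 is an extreme case.

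**The case against.** Unstratified permuted blocks are a valid design for a single-center trial. Chance imbalance can favor either arm, and the log-rank test already allows for it on average. This stands, and it limits the point to an improvement rather than an error.

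The choice of factor can be questioned. The Background's prognostic list describes what BCLC uses across all stages, including features that would exclude a patient here. Its only statement about predictors of local progression after ablation names poor differentiation and pretreatment AFP, not lesion number, and AFP is also measured before randomization. This also stands: the documents support lesion number as a reasonable stratum but do not single it out. What favors it is the structural link between ablated sites and the endpoint.

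The planned prognostic analyses already include multicentric disease and tumor number, so an adjusted look would not be wholly post hoc. That helps interpretation but leaves the primary test as it is.

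A reader might infer that about one trial in three will be visibly imbalanced. The documents do not support that as a plain statement, because it needs a multi-lesion share of roughly 25% or more and the plan gives none. A reader might also take the upper published rate, 24% per lesion with three lesions, and obtain a shift of 0.10 × (56.1 − 24.0) = 3.2 points. That rate in solitary tumors alone exceeds the 20% total event rate planned for MWA alone, so it does not fit the plan.

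**Conclusion.** The point holds as a low-cost improvement of minor weight. The main allocation and the primary test both ignore a baseline factor that the plan lists as prognostic and already collects. The chance of a 10-point or larger imbalance is about 13% to 36% for an assumed multi-lesion share of 10% to 40%. At the per-lesion risk compatible with the planned event rates, such an imbalance moves the estimate by about 0.9 to 1.8 points, well inside its standard error.

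It would be wrong to conclude that the primary comparison is biased or its type I error inflated, or that stratification would rescue the trial's power. Power is about 29% at 50 per arm because of the sample size, and stratification adds roughly 0 to 4 points, depending on how prognostic lesion number proves to be.

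**What to change.** Generate the variable-size blocks separately within two strata, solitary lesion versus 2-3 lesions on the pre-randomization CT or MRI, and prespecify the same two strata in the primary log-rank test. If the allocation list cannot be changed, stratify the log-rank test alone; in the simulation that separated the steps, this kept more than half of whatever gain there was. State the expected multi-lesion share. If the 2:1 fallback is kept, name lesion number among its covariates.

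The cost is one extra randomization list and one strata term in the analysis; no new procedure is needed. The downside is slightly unequal arm totals from incomplete blocks: with blocks of at most 6, at most 3 patients per stratum, or 6 overall.
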